The colonoscopy procedure for each patient will be no different from a conventional colonoscopy examination with excision of all polyps visualized and anatomopathological analysis, apart from a brief period of NBI analysis for each polyp detected prior to excision, enabling the polyp to be classified according to existing endoscopic classifications (i.e. NICE classification for adenomatous polyps and WASP classification for scalloped polyps).

This joint CHD-CHU project is original in that there are currently no data on the characterization of colonic polyps in NBI by large groups of "non-expert" endoscopists. Indeed, studies carried out to date on this subject, notably in the United States and England, have involved small numbers of NBI expert endoscopists. A recent "pilot" study carried out at Nantes University Hospital showed that NBI is becoming reliable, with a diagnostic accuracy of over 90%, for differentiating adenomatous polyps from typical hyperplastic polyps, but did not assess the contribution of NBI to the characterization of scalloped polyps, a still poorly understood entity. The technological improvement of endoscopes and the publication in 2016 of a classification (WASP) enabling the recognition of sessile scalloped polyps using NBI now necessitate evaluating the contribution of NBI for the recognition of these lesions. A study of this kind in general and university hospitals is essential to determine the feasibility of community implementation, with the ultimate aim of better detecting scalloped colonic lesions, which are often unrecognized but have a clearly demonstrated degenerative potential, and differentiating them from typical adenomatous polyps. The clinical gastroenterology departments of the CHD and CHU are very involved in clinical research, and collaborate on joint care and research projects. Both are equipped with the latest generation of Olympus and Fujifilm (for CHU de Nantes) systems with NBI, and have a significant endoscopic activity, notably in the field of colorectal cancer screening.

1. Justification of the study

1.1 Research positioning

Colorectal cancer is a major public health problem worldwide, particularly in industrialized countries. In France, the incidence of colorectal cancer ranked 3^e among all cancers, with 40,500 new cases and an estimated 17,500 deaths in 2011. (1). Most sporadic colorectal cancers arise from pre-cancerous lesions, adenomatous polyps, according to a now well-known carcinological development sequence (2). Colonoscopy combined with resection of adenomatous polyps reduces the risk of colorectal cancer (3,4). In France, colonoscopy is the reference method for colorectal cancer screening in populations selected as being at risk, according to the recommendations of the French National Authority for Health (HAS), and in patients suspected of having a colorectal neoplastic lesion in the presence of suggestive symptoms. (5).

Although colonoscopy is effective overall in reducing the risk of colorectal cancer, it is an imperfect tool, with 15-27% of lesions 'missed' and left in place (6,7), which can lead to the occurrence of interval cancers. Interval cancers are cancers that occur between two colonoscopies, and could account for up to 10.5% of colon cancers. They occur within 6 to 60 months (7). Among the possible causes of missed lesions, the involvement of adenomatous scalloped polyps currently raises major questions, as these lesions are still a poorly understood entity, but have a demonstrated degenerative potential (8). Their involvement in interval cancers is suggested both by their preferential right-sided location (the protective effect of colonoscopy being much less for the right colon than for the left), and by their lack of relief, which makes them more difficult to detect. Moreover, until recently, there was no clear endoscopic description enabling the endoscopist to recognize them and treat them effectively. As a result, the rate of incomplete endoscopic resections of scalloped adenomatous polyps is estimated at 30% (9).

From an anatomopathological point of view, the situation has become relatively complex in recent years, with the description of new colonic polyp entities (8). Historically, only conventional adenomatous polyps (at risk of degeneration) and typical hyperplastic polyps (without risk of degeneration) were distinguished, which explains why endoscopic classifications have focused on the ability to distinguish these 2 anatomopathological entities. The new WHO anatomopathological classification describes scalloped polyps, which it subdivides into 4 different morphological entities constituting evolutionary lesion spectra. The histological appearance of these lesions distinguishes between 1) typical hyperplastic polyps (reclassified as non-adenomatous scalloped lesions, and accounting for some 80-90% of scalloped lesions overall), 2) sessile scalloped adenomas/polyps, 3) sessile scalloped adenomas with dysplasia, and 4) traditional scalloped adenomas. While typical hyperplastic polyps have virtually no degenerative potential, other scalloped (adenomatous) lesions may degenerate. Descriptively, typical hyperplastic polyps are generally small and occur throughout the colon. Sessile scalloped polyps/adenomas do not show cytological lesions of dysplasia in the basal state. They are essentially characterized by abnormalities in the maturation of colonic crypt cells. They share many morphological features with hyperplastic polyps of the microvesicular subtype, in particular their predominantly right-sided location. They are generally larger than hyperplastic polyps. Foci of dysplasia identical to that of "classic" adenomas may appear in sessile scalloped polyps/adenomas. Sessile scalloped lesions with dysplasia are thought to progress more rapidly to adenocarcinoma than classical adenomas of equivalent dysplasia grade. Traditional scalloped adenomas are different from sessile scalloped lesions. They generally appear in the left colon and rectum, and are of villeinous or filiform architecture. They are characterized by the presence of a dysplasia rich in cells with penicillate eosinophilic cytoplasm and ectopic crypts not anchored to the

muscularis mucosa. Many of them are associated with a classic adenomatous component, and their evolutionary kinetics are identical to those of classic adenomas.

As far as endoscopy is concerned, it is accepted that, in routine practice, it is relatively easy to distinguish typical hyperplastic polyps from classic adenomas, thanks to optical advances. On the other hand, it remains very difficult to recognize adenomatous scalloped polyps. This poses a real problem, since adenomatous scalloped polyps are probably responsible for around 30% of colorectal cancers, including interval cancers (9). The best way to detect adenomatous scalloped polyps is therefore to learn how to recognize these lesions, which requires a high-quality optical examination and the use of optical filters such as Narrow Band Imaging (NBI).

A major challenge is therefore to distinguish conventional adenomatous polyps from scalloped lesions, particularly sessile adenomatous scalloped polyps. These lesions have an increased risk of developing colorectal cancer and represent around 12% of colonic polyps in a population referred for screening colonoscopy, but are often missed at colonoscopy due to their very flat nature.

These strategies require highly reliable optical prediction techniques during the endoscopic examination. However, standard diagnostic colonoscopy using white light, as currently practised, does not effectively differentiate between different polyp subtypes. Indeed, the diagnostic efficiency of white light for histological prediction of colonic polyps is only around 60-80%. (10). The most promising advances concern so-called "virtual chromoendoscopy" techniques such as Narrow Band Imaging (NBI) (Olympus and Fujifilm, Japan). With NBI, the image can be colored simply and immediately, at the touch of a button on the endoscope handle, to enhance mucosal microarchitecture and vessels. In technical terms, this involves the activation of an optical filter limiting the light spectrum to 2 specific wavelengths, 415nm (blue) and 540nm (green) respectively. As the two absorption peaks of hemoglobin occur at these wavelengths, the NBI allows blood vessels to appear darker, enabling better visualization of both mucosal surface details and capillaries. Several studies have demonstrated the value of NBI for characterizing colonic polyps, particularly small ones, with very good diagnostic accuracy and a high degree of confidence on the part of endoscopists. Indeed, these studies show diagnostic efficacy rates in the order of 96 to 98% for colonic polyps of 6 to 9mm, and 91 to 92% for those under 5mm (11-14).

The population of gastroenterologists around the world who could potentially use NBI is extremely large, since NBI has been available on all Exera (Olympus) and 760 (Fujifilm) series video processors for around 5 years in routine practice. However, published scientific data comes mainly from expert centers, and has been acquired by endoscopists with considerable expertise in the interpretation of NBI images. Moreover, analysis of published data is confounded by the multiplicity of classifications used, whose diagnostic criteria can vary significantly (15-17). Thus, all the following classifications have been proposed: Vascular Pattern Intensity (VPI), Sano classification, Hiroshima, Showa, etc. In order to standardize diagnostic criteria and harmonize practices, Tanaka and Sano proposed a new classification in 2011 called the NICE classification (Narrow band imaging International Colorectal Endoscopic) (18) which has been validated by other groups from expert centers (19) which differentiates between typical hyperplastic polyps and conventional adenomatous polyps (Figure 1), but did not include recognition of adenomatous scalloped polyps. Recently, the WASP classification has been developed for the diagnosis of scalloped adenomatous polyps, and appears extremely promising (20). This classification was published in Gut in 2016 (Figure 2), but no external validation study is currently available, nor is it currently underway to our knowledge. It therefore seems particularly interesting to evaluate this new classification, all the more so as studies carried out in the field of learning NBI semiology in general are in favour of relatively short learning curves (21-24).

Our aim is to evaluate and compare, using the CONECCT classification, the diagnostic performance of NBI for histological prediction of the nature of colonic polyps (conventional

adenomatous *versus* scalloped polyps) during colonoscopy, compared with histological analysis (taken as the reference method), in a large population of "non-expert" NBI endoscopists, after rapid and simple training in the NBI technique.

The gastroenterology clinical departments of the CHD and CHU collaborate on joint care and research projects. They are both equipped with the latest generation of Olympus and Fujifilm systems with NBI, enabling the use of appropriate classifications, and have significant endoscopic activity, particularly in the field of colorectal cancer screening.

This study in no way alters the patient's clinical management or care pathway. During colonoscopy in the presence of polyp(s) <20 mm, an observation sequence and image acquisition are performed in NBI, which does not significantly alter the duration of the endoscopic examination. The NBI is integrated into the high-definition endoscope (Olympus, Fujifilm) and the transition from white light to NBI is instantaneous.

Type I Hyperplasique

Type II Adénome

Figure 1: NICE (Narrow band imaging International Colorectal Endoscopic) **classification.** Diagnostic criteria in favor of a typical hyperplastic polyp (type I) are: a) absence of dark appearance of the polyp in relation to the adjacent mucosa, b) absence of brownish vessels, c) absence of oval structures within the polyp.

Conversely, the presence of one or more of the above-mentioned criteria is indicative of a conventional adenomatous polyp (type II).

Figure 2: WASP (Workgroup Serrated PolypS and Polyposis) **classification**. Diagnostic criteria in favor of an adenomatous scalloped polyp are: a) the existence of a cloudy appearance of the polyp, b) an irregular shape, c) the presence of black spots within the colonic glands.

CONECCT	IH Hyperplasique	IS Lésion festonnée sessile	IIA Adénome simple	IIC Adénome à risque ou cancer superficiel	III Adénocarcinome profond
Macro	Souvent petits <10 mm Surélevé Ila	Paris IIa ou IIb Limites imprécises en nuage ou en plateau	Paris Ip, Is Ou Ila Rarement déprimé	Souvent IIc Ou IIa + IIc Ou LST Non granulaire Ou macronodule (> 1cm) sur LST Granulaire	Souvent III Ou IIc avec composant nodulaire dans la dépression Saignements spontanés
Couleur (NBI ou équivalent)	Claire ou équivalente au background	Variable Mucus jaune (rouge en NBI)	Foncée par rapport au background	Foncée souvent	Hétérogène, foncées ou très claires par zones
Vaisseaux (NBI ou équivalent)	Absence de vaisseaux ou vaisseaux fins ne suivant pas les cryptes	Absents parfois Spots noirs au fond des cryptes rondes	Réguliers Suivant les cryptes allongées	Irréguliers mais persistants Pas de zone avasculaire	Irréguliers Gros vaisseaux interrompus Ou absents (zones avasculaires)
Cryptes (chromo virtuelle ou réelle)	Rondes Blanches	Cryptes rondes points noirs (NBI)	Allongées Ou Branchées Cérébriformes régulières	Irrégulières mais conservées Pas de zone amorphe	Absentes Détruites Ou irrégulières dans une zone délimitée (démarcation nette)
Résection	Pas de résection	EN BLOC RO PIECE MEAL si non r	•	EN BLOC R0 (EMR ou ESD (>20 mm)	CHIRURGIE avec curage

Figure 3: CONECCT classification (Colorectal Neoplasia Classification to Choose the Treatment).

1.2 Benefits and risks for research subjects

1.2.1 Benefits

The results of this research will contribute to the development of knowledge in the field of pathology.

1.2.2 Risks

- **NBI prediction**: poor lesion targeting, erroneous use of NBI methodology and tests (despite learning) leading to misdiagnosis.

- The risk associated with **histological analysis** is not specific to this study, but applies to all procedures for processing, reading and interpreting histological specimens. It relates to malfunctions and quality defects at various stages (preparation, staining....), and can lead to misdiagnosis.

- **Associated procedures**: the risks of colonoscopy and biopsies are those incurred when these examinations and techniques are carried out as part of everyday practice, i.e. pain, bleeding, perforation and infectious risks.

- Added to this are the risks associated with **drugs administered for colonic preparation** and those administered for **anesthesia/analgesia** during and after the examination. These risks are described in the SPCs of the drugs concerned, administered within the scope of their marketing authorization.

- **Pathology under study**: colorectal cancer screening/risk monitoring: risk of underdiagnosis and latent progression.

1.2.3 Justification for positioning as research with minimal risks and constraints

The person in charge of the research qualifies it in first intention as **interventional research with minimal risks and constraints**, since :

All procedures are routinely performed (colonoscopy) and defined in the order of April 12, 2018 set by the Ministry.

Research does not focus on innovative or obsolete techniques or strategies.

Apart from the transition to NBI, all patient management will be identical to usual practice. In particular, the date of discharge will be decided by the doctor in charge of the patient, independently of the study, but will be recorded in the patient file and the research CRF.

As a result, the particular conditions under which the research is carried out represent negligible constraints for the person undergoing the research. (Article R 1121-3 of the French Public Health Code (CSP), decree no. 2006-477 of April 26, 2006)

Before any research is carried out, the person in charge of the research will submit the study protocol to the Comité de Protection des Personnes Ouest III de Poitiers for a favorable opinion and confirmation of the research's qualification, in accordance with article L 1121-1 of the French Public Health Code (CSP), as amended by laws no. 2004-806 of August 9, 2004 and no. 2006-450 of April 18, 2006 relating to public health policy.

Bibliographical references are appended to the document.

2. Objectives and endpoints

2.1 Objective and primary endpoint

2.1.1 Primary objective

To evaluate the diagnostic performance of the NBI for the characterization of scalloped colonic polyps of all types [typical hyperplastic and adenomatous scalloped; i.e. CONECCT IH and CONECCT IS] versus conventional adenomatous [i.e. CONECCT IIA] during colonoscopy in a population of "non-expert" endoscopists.

2.1.2 Primary endpoint

Sensitivity of NBI compared with histological analysis (=reference method). Number of polyps characterized as scalloped (CONECCT IS) on reading by NBI compared with the number of polyps characterized as scalloped on standard histology.

2.2 Objectives and secondary endpoints

2.2.1 Secondary objectives

 Measurement of diagnostic performance indices (specificities, PPV, NPV) using NBI and white light alone for characterization of polyps CONECCT IH and IS versus CONECCT IIA

Within scalloped polyps (according to pathological analysis results), diagnostic capabilities (sensitivities, specificities, PPV, NPV) of NBI and white light alone to characterize CONECCT IS polyps.

- Comparison of the diagnostic performance of NBI and white light alone for the characterization of polyps CONECCT IH and IS versus CONECCT IIA
- Diagnostic performance by degree of certainty in NBI.
- Evaluation of the role of endoscopist seniority in polyp characterization in NBI.
- Assessment of the role of polyp size in polyp characterization.

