4.2.2 Description of techniques and analyses

Study diagram :

- All endoscopists participating in the study will receive an initial one-hour training course in NBI polyp characterization, delivered by an expert endoscopist in image analysis ([name] [name], graduate of the DIU 'Endoscopie Diagnostique Avancée').
- A verification test (rate of correct answers >95%) will be carried out before each operator is authorized to take part in the study, based on an independent set of images of 30 colonic polyps.
- Each patient corresponding to the pre-inclusion criteria and agreeing to take part in the study is "pre-included". During colonoscopy, the presence of any polyp(s) smaller than 20mm is determined. The right colon, which is the preferred site for adenomatous scalloped polyps, will be examined with particular attention by a second pass under white light. This 2^{ème} pass is routinely performed in standard practice, for example to check fast-moving areas during colonoscopy, and will only increase examination time by around 2-3 minutes. Patients without a polyp smaller than 20 mm are not included in the study.

- Each polyp measuring less than 20mm will be analyzed in white light and NBI, as follows:
- 1) White-light image analysis

2) Switch to NBI mode by simply pressing the 'NBI' button on the endoscope handle (immediate acquisition of the NBI image with photographic recording in LB and NBI). A prediction of the histological type of polyp according to the CONECCT classification is made by the endoscopist and noted in the CRF, together with the degree of certainty (strong or weak).

The study is limited to 4 polyps per patient. Only data from the first 4 polyps removed will therefore be collected.

- All polyps detected and analyzed by NBI are then removed by excision (forceps excision, mucosectomy) according to the usual procedure and analyzed by conventional histology (gold standard).
- If it is impossible to characterize a polyp by NBI (image of poor quality or diagnosis impossible), the examination will be considered a technical failure of NBI, but the polyp will be removed for histological analysis in accordance with current recommendations.
- If the polyp is not recovered for histological analysis, or if interpretation is impossible (coagulation artifacts after standard resection, for example), the examination will be considered a technical failure of standard histology.

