5.2 Statistics

Responsible for statistical analysis: [name] [name]

5.2.1 Description of planned statistical methods, including schedule of planned interim analyses and statistical justification of number of inclusions

Analysis of primary endpoint:

Sensitivity of the NBI technique to pathological findings for the characterization of colonic polyps (conventional adenomatous [CONECCT IIA] versus scalloped [CONECCT IS]) at colonoscopy will be calculated with its 95% confidence interval.

Secondary endpoints :

- The diagnostic performance (specificity, positive predictive value, negative predictive value, RV+, RV-, diagnostic accuracy (corresponding to the rate of correct responses)) of NBI for the characterization of colonic polyps (conventional adenomatous [CONECCT IIA] versus scalloped [CONECCT IS]) compared with standard histology will be estimated with their 95% confidence interval.

- The sensitivity and specificity of white light compared with standard histology results will be estimated with a 95% confidence interval and compared with those obtained by NBI using a McNemar test.

- If numbers permit, sensitivity analyses will be carried out:

- The sensitivity of NBI for the characterization of CONECCT IH and IS polyps versus CONECCT IIA will be estimated according to the certainty of the polyp characterization in NBI: strong or weak. These 2 sensitivities will be compared using a Chi2 test.

- The same analysis will be carried out on the seniority of the endoscopist: junior or senior.

- The same analysis will be performed according to polyp size: 1-5mm vs. 6-9mm vs. 10-20mm or 1-5mm vs. 6-20mm depending on numbers.

Number of subjects required :

Over 48 months, we plan to include 690 patients at Nantes University Hospital and the CHD de Vendée, with the aim of characterizing at least 690 polyps measuring less than 20 mm. About 50% of these will be CONECCT IIA polyps, 40% CONECCT IH and 10% CONECCT

IS. In addition, a majority of these polyps will be <5 mm in size (\approx 60%), \approx 30% between 6-9 mm and \approx 10% >10mm.

Assuming that 5% cannot be analyzed, and that the sensitivity of the NBI is 90%, we can estimate our sensitivity with a confidence interval of \pm 3%.

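### PPV and NPV of an IS call are planned only among histologically scalloped polyps, so adenomas called IS are not counted as false positives and the PPV is overstated whenever there are any

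*Combined protocol and SAP*

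**What the plan says.** Section 2.2.1 lists, for recognising CONECCT IS: "Within scalloped polyps (according to pathological analysis results), diagnostic capabilities (sensitivities, specificities, PPV, NPV) of NBI and white light alone". The denominator is therefore set by the pathology result. Section 2.1.1 fixes what scalloped means: "scalloped colonic polyps of all types [typical hyperplastic and adenomatous scalloped; i.e. CONECCT IH and CONECCT IS] versus conventional adenomatous". IH and IS are in; IIA is out.

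Two other planned analyses give predictive values:
- Section 2.2.1 also plans "Measurement of diagnostic performance indices (specificities, PPV, NPV) using NBI and white light alone for characterization of polyps CONECCT IH and IS versus CONECCT IIA". This treats IH and IS as one class.
- Section 5.2.1 plans PPV, NPV, likelihood ratios and accuracy of "NBI for the characterization of colonic polyps (conventional adenomatous [CONECCT IIA] versus scalloped [CONECCT IS]) compared with standard histology will be estimated". This names IIA and IS, but not IH.

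Section 5.2.1 describes no method for the within-scalloped objective. For white light it mentions only sensitivity and specificity.

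On timing, section 4.2.2 says: "A prediction of the histological type of polyp according to the CONECCT classification is made by the endoscopist and noted in the CRF". The polyp is removed and sent to pathology afterwards. On the expected mix, section 5.2.1 says: "About 50% of these will be CONECCT IIA polyps, 40% CONECCT IH and 10% CONECCT" IS.

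**The concern.** A predictive value answers a question asked at the time of the call: given that the endoscopist says IS, how often is histology IS? It should condition on the call alone. The objective in 2.2.1 conditions on part of the reference result as well. A conventional adenoma called IS is a wrong IS call, but histology places it outside the subset and it disappears from the PPV denominator. The class removed is the largest one in the expected mix.

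The error at issue is one the study cares about. Section 1.1 presents the separation of conventional adenomas from scalloped lesions, sessile adenomatous ones in particular, as a main challenge, and the operators are non-expert by design. A reader who takes the reported PPV as the reliability of an IS call at colonoscopy would be given too favourable a figure for both NBI and white light.

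**Working it through.** **The plan's own figure.** The documents state no PPV or NPV. The one precision figure is ±3% for a sensitivity of 90%, with 690 polyps and 5% not analysable. With IH plus IS as the denominator:
- n = 690 × 0.95 × 0.50 = 327.75
- half-width = 1.96 × √(0.9 × 0.1 / 327.75) = 3.25%, which rounds to ±3%

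With IS alone, n = 65.55 and the half-width is 7.26%. The stated 90% therefore fits the pooled scalloped class. Using it as the sensitivity for IS, as below, is an assumption.

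**Inputs from section 5.2.1.** "with the aim of characterizing at least 690 polyps measuring less than 20 mm", less 5%, gives 690 × 0.95 = 655.5 analysable polyps:
- IS: 10% = 65.55
- IH: 40% = 262.2
- IIA: 50% = 327.75

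**Inputs that are assumptions.** Se = P(called IS | IS) = 0.90; f1 = P(called IS | IH) = 0.10, that is, 90% specificity against IH; f2 = P(called IS | IIA), varied from 0 to 10%. The documents give neither f1 nor f2.

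**Formulas.**
- PPV within scalloped = 0.10·Se / (0.10·Se + 0.40·f1)
- PPV over all polyps = 0.10·Se / (0.10·Se + 0.40·f1 + 0.50·f2)

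The two differ only by 0.50·f2 in the denominator, so the first exceeds the second for every f2 > 0 and equals it at f2 = 0.

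**PPV.** True positives = 65.55 × 0.90 = 59.0. False positives from IH = 262.2 × 0.10 = 26.2. Within scalloped: 59.0 / 85.2 = 69.2%.

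| IIA called IS | False positives from IIA | PPV over all polyps | Excess of within-scalloped PPV |
|---|---|---|---|
| 0% | 0 | 69.2% | 0 points |
| 2% | 6.6 | 59.0 / 91.8 = 64.3% | 4.9 points |
| 5% | 16.4 | 59.0 / 101.6 = 58.1% | 11.2 points |
| 10% | 32.8 | 59.0 / 118.0 = 50.0% | 19.2 points |

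**NPV.** False negatives = 65.55 × 0.10 = 6.6, the same in both tables. True negatives from IH = 262.2 × 0.90 = 236.0. Within scalloped: 236.0 / (236.0 + 6.6) = 97.3%. Over all polyps at f2 = 5%, true negatives are 236.0 + 311.4 = 547.3, giving 547.3 / 553.9 = 98.8%. At 2% and 10% it is also 98.8%.

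**Sensitivity to the assumptions.** At f2 = 5% and Se = 0.90, the PPV excess is 15.2, 11.2 and 6.8 points for f1 = 0.05, 0.10 and 0.20. Over Se 0.7 to 0.9, f1 0.05 to 0.20 and f2 1% to 10%, it runs from 1.5 to 27.8 points.

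**Do the other planned contrasts supply the figure?** The IH+IS versus IIA contrast counts an adenoma called IS as an error, but does not separate an IS call from an IH call. The IIA versus IS contrast, taken literally, counts the IIA false positives and leaves out the IH ones. At Se = 0.90 and f2 = 5% it gives 59.0 / (59.0 + 16.4) = 78.3%, against 58.1% over all polyps when f1 = 0.10. Neither is the PPV of an IS call over all analysed polyps.

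**The case against.** The strongest reply is that the subset is deliberate and disclosed. The objective states its denominator and follows one that separates scalloped polyps from adenomas, so a two-step layout (scalloped or not, then IS or IH) is a natural reading. This stands for sensitivity and specificity, which already condition on histology and are valid for IS versus IH in that subset. It does not rescue PPV and NPV: a second step usable at colonoscopy would condition on the endoscopist's scalloped call, whereas the text conditions on pathology.

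A reader might infer that adenomas called IS drop out of the study altogether. The documents do not support that: both contrasts against IIA count such errors. What is missing is narrower, namely one predictive value that sets an IS call against every other histology.

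A reader might also infer that the within-scalloped PPV is meaningless, or that the whole picture of NBI is flattered. That goes too far as well. It is a correctly computed figure for a stated subset, it equals the all-polyp value if no adenoma is called IS, and NPV moves in the unfavourable direction.

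The size is uncertain, and this objection stands. With about 85 IS calls, the 95% half-width around a PPV of 69% is 1.96 × √(0.692 × 0.308 / 85.2), about 10 points (polyps treated as independent), so the 2% scenario lies within sampling error. The discrepancy is systematic, however, and would not shrink with more polyps.

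Finally, section 5.2.1 is silent on this objective, so how it would be carried out is not certain. Section 2.2.1 is the only specification there is.

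**Conclusion.** The point holds for two of the four indices in one secondary objective. As worded, PPV of an IS call is overstated whenever any conventional adenoma is called IS, and NPV is somewhat understated. The direction of the PPV error is algebraic. Its size rests on the plan's 50/40/10 mix and on three assumed rates: IS sensitivity, specificity against IH, and the share of IIA called IS. In the base case the PPV excess is about 5, 11 or 19 points at 2%, 5% or 10% of IIA called IS, and nil at 0%; NPV is low by about 1.5 points. The primary sensitivity is unaffected, as are sensitivity and specificity of IS versus IH within scalloped polyps. That specificity says nothing about adenomas. The change is worth making before analysis, but it does not bear on the primary result.

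**What to change.** In section 2.2.1, keep sensitivity and specificity of IS versus IH within histologically scalloped polyps. Take PPV and NPV out of that subset and define them for an IS call over all analysed polyps: histological IS versus every other histology, with any non-IS call counted as test-negative, for both NBI and white light. Add the same definition to section 5.2.1, which at present has no method for this objective. A full cross-table of endoscopic against histological CONECCT class would let readers see where the wrong IS calls come from.

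The cost is about one sentence in each section. Section 2.2.2 already collects the white-light, NBI and histological class of each polyp, and the analysis set in section 5.2.5 already covers all polyps characterised by NBI and histology. The drawback for the sponsor is a less favourable reported PPV.
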